3 POPULATIONS FOR ANALYSIS

The Enrolled Set (ES) will consist of all study participants who have given informed consent.

The Randomized Set (RS) will consist of all randomized study participants.

The Safety Set (SS) will consist of all study participants who receive ≥ 1 dose of IMP (bimekizumab or placebo).

The Full Analysis Set (FAS) will consist of all randomized study participants who receive ≥ 1 dose of IMP and have a valid measurement for each of the co-primary efficacy endpoints at Baseline.

The Active Medication Set (AMS) will consist of all study participants who receive ≥ 1 dose of active IMP (bimekizumab).

The Maintenance Set (MS) will consist of all study participants who receive ≥ 1 dose of active IMP (bimekizumab) in the Maintenance Treatment Period.

The Per-Protocol Set (PPS) will consist of all study participants in the RS who have no important protocol deviations affecting the co-primary efficacy endpoints. Important protocol deviations

will be predefined, and study participants with important protocol deviations will be evaluated during ongoing data cleaning meetings prior to database lock. The classification of PPS will be determined at blinded data evaluation meeting before unblinding of the data. The classification of study participants with important protocol deviations related to treatment group information will be re-determined after general unblinding.

The Pharmacokinetics Per-Protocol Set (PK-PPS) will consist of all randomized study participants who receive ≥ 1 dose of active IMP (bimekizumab) and provide ≥ 1 quantifiable plasma concentration post dose without important protocol deviations that would affect the concentration.

4 STATISTICAL ANALYSES

4.1 General considerations

All analyses will be performed using SAS[®] version 9.4 (SAS Institute, Cary, NC, US). All tables and listings will use Courier New font size 9.

Descriptive statistics will be displayed to provide an overview of the study results. For continuous variables, descriptive statistics will consist of number of the study participants with available measurements (n), mean, standard deviation (SD), median, minimum, and maximum.

For categorical variables, the number and percentage of study participants in each category will be presented. Unless otherwise noted, the denominator for percentages should be based on the number of study participants included in the respective analysis set. Study participants with missing data will be accounted for using the following approaches:

- For summaries of demographics and Baseline characteristics: summarize percentages based on all study participants in the analysis set and include a “Missing” category (corresponding to study participants with missing data for the variable being summarized) as the last row in the list of categories being summarized.
- For summaries of efficacy and safety endpoints, unless otherwise specified: summarize percentages based only on those study participants with observed data for the variable being summarized. As the denominator may be different from the number of study participants in the analysis set being considered, the denominator should be displayed in the table. The general format for displaying this will be “n/Nsub (%)”.

Percentages will be presented to 1 decimal place. If the percentage is 100%, do not present a decimal. If the percentage is 0, do not present the percentage. Typically, the % sign should be presented in the column header, but not with each individual value.

For bimekizumab PK concentrations, descriptive statistics will include geometric mean, geometric coefficient of variation (CV), 95% confidence intervals (CIs) for geometric mean, arithmetic mean, SD, median, minimum, and maximum. All summaries of PK variables will be based on the observed values. No imputation will be used.

Decimal places for descriptive statistics will always apply the following rules:

- “n” will be an integer
- Mean, SD, and median will use one additional decimal place compared to the original data

- CV [%] will be presented with one decimal place
- Minimum and maximum will have the same number of decimal places as the original value.

Derived variables in general will display the mean, SD and median to 1 more decimal place than the variables used in the derivation. If the number of decimal places reported in the raw data is varied then use either the maximum raw number of reported decimal places or 3, whichever is the lowest, as a guide for the descriptive statistics.

Statistical tests of efficacy variables will be presented as two-sided p-values rounded to three decimal places. P-values less than 0.001 will be presented as “<0.001” and p-values greater than 0.999 will be presented as “>0.999”. Statistical comparisons will be two-sided and will be performed at the 0.05 level of significance.

A complete set of data listings containing all documented data as well as calculated data (eg, change from Baseline) will be generated.

Unless otherwise stated, the IMP administration in the Maintenance Treatment Period includes both active IMP (bimekizumab) and placebo injections for study participants randomized to BKZ Q4W in the initial treatment period and switch to BKZ Q8W in the Maintenance Treatment Period.

Per protocol, for visits from the first dose of IMP through Week 32, the visit window is ± 4 days from the scheduled visit. For the SFU Visit, the visit window is ± 7 days from the scheduled visit. All by-visit summaries will contain nominal (ie, scheduled) visits only. Unscheduled visits will not be mapped to scheduled visits except for assessments that occur within a 4-day time window of a scheduled visit and the relevant scheduled visit data is not available. In that case, the assessment will be mapped to the corresponding scheduled visit and will be used for the analysis. If multiple unscheduled visits are remapped to one scheduled visit, the data collected on a day nearest to the scheduled visit day will be used in the analysis. This will only occur for some vendor data (questionnaire data such as PASI, IGA, PSD, scalp IGA, and DLQI data).

4.1.1 Analysis time points

4.1.1.1 Relative day for listings

Relative day will be included in different listings and will be calculated as follows:

- If the event occurred on or after the date of first IMP administration and on or prior to the date of last IMP administration, then the following calculation is used:

$$\text{Relative Day} = \text{Date}_x - \text{Date of first dose} + 1$$

where Date_x is the start or stop date of interest and Date of first dose is the date of first IMP administration.

- If the event occurred before the date of first IMP administration, then the following calculation is used:

$$\text{Relative Day} = \text{Date}_x - \text{Date of first dose}$$

Relative days that occur before the date of first IMP administration should be preceded by a “-”.

- If the event occurred after the date of last IMP administration, then the following calculation is used:

$$\text{Relative Day} = \text{Date}_x - \text{Date of last dose}$$

where Date_x is the start or stop date of interest and Date of last dose is the date of last IMP administration. Relative days that occur after the date of last IMP administration should be preceded by a “+”.

Relative day will only be computed for fully completed dates and will be missing for partial dates.

4.1.1.2 Analysis periods

The following study periods are defined:

- Screening Period: starts at the time of the informed consent date and ends one day before the first IMP administration.
- Initial Treatment Period (ITP): starts on the day of the first IMP administration and ends prior the first IMP administration in the maintenance treatment period (first IMP in the maintenance treatment period typically occurs at Week 16, but for those that miss the Week 16 IMP administration, first IMP in the maintenance treatment period will be the first IMP administration after Week 16). For study participants that withdraw from the study prior to start of IMP in the maintenance treatment period, the ITP ends on the day of the PEOT Visit. If the PEOT visit is not done, the ITP end date will be set to the date of premature study termination.
- Maintenance Treatment Period (MTP): starts on the day and time of the first IMP administration in the MTP (first IMP in the MTP typically occurs at Week 16 after all clinical and safety assessments have been completed, but for those who miss the Week 16 IMP administration, first IMP in the MTP will be the first IMP administration after Week 16) and ends at the Week 32 visit. For study participants withdrawn from the study after Week 16 but before Week 32, the MTP will end at the PEOT Visit. If the PEOT visit is not done, the MTP end date will be set to the date of premature study termination.
- SFU Period: for participant who complete the study, in other words, complete all scheduled visit, up to and including Week 32, the SFU period starts on the day after Week 32 and ends on the day of the SFU visit. For participants who withdraw early from the study the SFU period start on the day of after PEOT Visit and ends on the day of the SFU visit.

Study participants will be considered to have completed a period if they complete the last scheduled study visit including the respective assessments for that period. It is possible for a study participant to discontinue the study after the Week 16 visit without entering the MTP. Therefore, study participants who discontinue after Week 16 assessments and who never start the MTP will be counted as having completed the ITP but having discontinued the overall study. If study participants miss the Week 16 visit, but start treatment in the MTP, they will still be considered to have completed ITP.

A study participant will be considered to have completed the study if he/she completes all scheduled visits, up to and including Week 32 (regardless of completion of the SFU Visit).

4.1.2 Definition of baseline values

A Baseline value for a study participant is defined as the latest measurement for that study participant up to and including the day of first IMP administration, unless otherwise stated. If a Baseline assessment is taken on the same day as first IMP administration, it is eligible to be used as the Baseline value, even in the case that the time of the assessment is recorded as taking place after the time of first IMP administration. This is considered acceptable as this measurement is still the best representation of the Baseline value of the given assessment since it is highly unlikely that the IMP could have an impact on any measurement in such a short period of time. However, such cases should be rare as study center personnel are instructed to do all assessments at the Baseline visit prior to administering IMP. One exception to this rule is plasma concentration. If Baseline plasma concentration is measured at a time after the first IMP administration, then it should not be eligible to be considered as a Baseline plasma concentration. Such cases should be discussed with the quantitative clinical pharmacologist. If a Baseline measurement is missing or not collected, and a Screening value is available, the Screening value will be utilized as Baseline instead.

Baseline values for component scores should be computed using components from the same visit where the relevant measurements were recorded prior to dosing. For example, if the component scores on the Baseline visit cannot be derived due to missing components, the Baseline value for the component score should be calculated using the Screening visit values if the Screening visit has all of the components.

4.1.3 Mapping of assessments performed at Early Discontinuation Visit

If the PEOT visit occurs at a scheduled visit as outlined in the schedule of assessments, then no mapping is necessary, and any PEOT assessments should correspond to that scheduled visit. PEOT visit assessments that occur on a date after a scheduled visit will be assigned to the next scheduled site visit per the protocol following the last visit where assessments were available regardless of the given assessment actually collected per the protocol SoA.

This approach means that there is a chance that data will be mapped to a visit where a given assessment was not actually collected per the protocol SoA. If that happens, those data will not be summarized in by-visit tables (though they will be available in the listings).

The only exception to the above rule is for anti-bimekizumab antibody assessments, in which all PEOT visit assessments will be assigned to the next scheduled visit at which anti-bimekizumab antibody are assessed.

All by-visit summaries will contain nominal visits only. Unscheduled visits will not be mapped to scheduled visits. However, in cases where vendor data (questionnaire data such as PASI, IGA, PSD, scalp IGA, and DLQI data) is assigned to an unscheduled visit instead of a scheduled visit, the assessments will be mapped into the scheduled visit if the assessments dates fall into the permissible window, as detailed in Section 4.1.

Note that based on the early withdrawal mapping conventions described above, a mapped PEOT visit is considered as observed at that visit and should be summarized as such in the tables.

4.1.4 Treatment assignment and treatment groups

It is expected that study participants receive treatment as randomized for the ITP, or as assigned per protocol study design (via reallocation) for the MTP.

Safety analyses will be based on the SS, as randomized. However, if after unblinding it is determined that study participants randomized to placebo received bimekizumab at any time within the first 16 weeks, then for safety analyses these study participants will be reallocated to the appropriate bimekizumab treatment group, unless otherwise specified. Study participants randomized to bimekizumab will only be reallocated to the placebo treatment group if they never received bimekizumab.

Unless otherwise stated, the summary tables of safety analyses will be provided as:

- The ITP data will be displayed by Placebo and BZK 320mg Q4W columns based on the SS
- The MTP data will be displayed by BKZ 320mg Q4W and BKZ 320mg Q8W columns based on the MS by treatment received at the MTP
- The initial and maintenance treatment period data will be displayed by BKZ 320mg Q4W, BKZ 320mg Q8W, and BKZ 320mg Total columns based on the AMS

Study participants randomized to BKZ 320mg Q4W and received BKZ 320mg Q8W in the MTP will be represented in both the BKZ 320mg Q4W and BKZ 320mg Q8W treatment columns. BKZ 320mg Q8W column only presents the data after the switch from BZK 320mg Q4W to BKZ 320mg Q8W. BKZ 320mg Q4W column will also include study participants that switch from Placebo to BKZ 320mg Q4W (only data after switch).

Efficacy analyses should be performed according to randomized treatment and not actual treatment received.

Unless otherwise stated, the summary tables of efficacy analyses will be provided as:

- The ITP data will be displayed by Placebo and BZK 320mg Q4W columns based on the RS
- The MTP data will be displayed by BKZ 320mg Q4W column and BKZ 320mg Q8W column based on the MS by treatment received at the MTP
- The initial and maintenance treatment period data will be displayed by Placebo/BKZ 320mg Q4W and BZK 320mg Q4W/Q8W columns based on the randomized treatment sequence by RS

For all TFLs for demographics, baseline disease characteristics, previous and ongoing medical history, prior and concomitant medications, and psoriasis treatment history, the summary will be displayed by Placebo/BKZ 320mg Q4W and BKZ 320mg Q4W/Q8W columns based on the randomized treatment sequence.

4.1.5 Multicenter studies

The data from all centers will be pooled for the purposes of the analysis. No exploration of treatment by center interaction will be investigated.

4.1.6 Center pooling strategy

All centers will be pooled together for the analysis. No special centers pooling strategy is planned for this study.

4.2 Primary endpoints analysis

The co-primary efficacy endpoints for this study are PASI90 response and IGA 0/1 response at Week 16.

4.2.1 Definition of endpoints

4.2.1.1 PASI90 response at Week 16

PASI90 response at Week 16 is defined to be equal to 1 if the percentage improvement from Baseline to Week 16 in the PASI scores is 90% or greater and 0 if the percentage improvement from Baseline to Week 16 is less than 90%. This definition is introduced for the purpose of identifying study participants who respond to the treatment (1 = responder, 0 = non-responder).

Detailed information of PASI scores and the definition of percentage improvement from Baseline can be found in Section 6.8.2.

4.2.1.2 IGA 0/1 response at Week 16

IGA 0/1 response at Week 16 is defined as clear [0] or almost clear [1] with at least a two-category improvement from Baseline at Week 16.

Detailed information of IGA can be found in Section 6.8.3.

4.2.2 Main analytical approach

The coprimary efficacy endpoints will be analyzed for all study participants in the RS. The primary analysis will be based on the Cochran-Mantel-Haenszel (CMH) test. Treatment comparisons will be made based on the CMH test using the p-value for the general association. Odds ratios and associated 95% CIs based on the Wald test will also be presented. Risk difference and associated 95% CI based on the Wald asymptotic between bimekizumab and placebo will be provided. If one of the treatment groups has 0 or very low response where CMH is no longer an appropriate method, Fisher's exact method will be applied instead, odds ratio and associated 95% CI will not be provided.

Non-responder imputation (NRI) will be used to account for missing data in the primary analysis. Specifically, any study participant who permanently withdraws from IMP prior to Week 16 or who has missing data for the co-primary efficacy variables at the Week 16 time point will be considered as a non-responder.

[figure not shown]
The number and percentage of study participants who are PASI90 responders at Week 16 will be summarized for the RS. IGA0/1 response will be summarized in the same manner as the PASI90 response.

Line plots of the mean percentage improvement from Baseline in PASI score over time by treatment group will be produced.

Line plots of the PASI90 and IGA0/1 responder rate over time by treatment group will be produced.

By-study participant listings of PASI and IGA responder variables, PASI and IGA data will be provided for the RS.

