| | | Section 4.5.3.1: criteria for nR calculation is updated | Updated to correct the typo. |

| SAP Version | Date | Change | Rationale |
|-------------|-------------|---|---|
| | | Section 4.5.3.2: body temperature is added | Updated as body temperature was collected in the study. |
| | | Section 6.2, WHODD version is updated | Updated to be consistent with the latest BKZ program convention. |
| | | Section 6.3, 6.4: MS is added. Section 6.4.2: wording is updated | Updated as MS was defined for analysis of MTP based on study participants entering MTP. |
| | | Section 6.12: algorithmic is updated per the latest standards | Updated to be same with the latest BKZ program convention. |
| | | Section 7: reference is added | Updated to add one new reference. |
| 1.4 | 30 Jul 2024 | Section 4.1.4: add "by treatment received at the start of the MTP" | Updated to provide clarity. |
| | | Section 4.5.1: algorithmic is updated for time at risk for combined treatment period | Updated to clarify the algorithms. |
| | | Section 4.5.2.4.2: added back "Any Malignancy excluding non melanomic skin cancers" Section 4.5.2.2: a listing for device deficiency is added | Updated to reflect the correct rule. |
| 1.5 | 6 Aug 2024 | Section 4.1: clarification is added (IMP means both bimekizumab and placebo). Section 4.5.1.3: logic is updated to follow pivotal study Section 6.8.1.1: clarification is added to define missing data in efficacy analysis | Updated to provide clarity. |
| Amend-1 | 14 Aug 2024 | Clean version to be finalized | |

| SAP Version | Date | Change | Rationale |
|-------------|-------------|--|--|
| Amend-2 | 21 Nov 2024 | 
Section 4.1.1.2
 
Additional rules have been incorporated into the definitions of the ITP and MTP study periods:
 
For ITP: If the PEOT visit is not done, the ITP end date will be set to the date of premature study termination.
 
For MTP: If the PEOT visit is not done, the MTP end date will be set to the date of premature study termination.
 | These rules are added to address scenarios where the PEOT visit is not conducted |
| | | 
Section 4.2.2
 
Section 4.2.3.1
 
Section 4.3.1.2
 
In the circumstance where Fisher's exact test will be applied instead of the CMH test, the risk difference and its 95% will still be provided.
 | When Fisher's exact test is applied, the calculation of the risk difference and its associated 95% confidence interval remains feasible. |

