4.3.1.2 Main analytical approach

The key secondary efficacy endpoints will be analyzed for all study participants in the RS. The primary analysis will be based on the CMH test as specified in Section 4.2.2. If one of the treatment groups has 0 or very low response where CMH is no longer an appropriate method, Fisher's exact method will be applied instead, odds ratio and associated 95% CI will not be provided.

NRI will be used to account for missing data in the primary analysis. Specifically, any study participant who permanently withdraws from IMP prior to the given time point of interest or who has missing data for the key secondary efficacy variables at the given time point of interest will be considered as a non-responder.

The number and percentage of study participants who are PASI75 responders at Week 4 and PASI100 responders at Week 16 will be summarized separately for the RS.

Line plots of the PASI100 responder rate over time by treatment group will be produced.

By-study participant listings of PASI75 and PASI100 responder variables will be provided for the RS.

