The corresponding CI for the risk difference is as follows:

$$CI_{RD} = RD \pm Z_{1-\alpha/2} \times (SE_{RD})$$

where $Z_{1-\alpha/2}$ is the Z statistic for the corresponding level of alpha. For the risk difference CIs calculated in this SAP, 1.96 will be used (corresponding to a two-sided alpha of 0.05 and 95% CI). The risk difference and corresponding CI will be displayed as percentage.

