4.5.2.2 AE summaries

The following summaries will be provided in three different ways: by treatment for the ITP for the SS, by treatment for the MTP for the MS, by treatment for the Initial and Maintenance Treatment Period (combined) for the AMS. For summaries for the ITP, MTP, and Initial and Maintenance Period (combined), the TEAEs will be attributed according to their onset date and time at risk of each study participants for each period (see Section 4.5.1).

- Incidence of TEAEs – Overview
- Incidence of TEAEs per 100 participant years by SOC, HLT, and PT

The following summaries will be provided in two different ways: by treatment for the ITP for the SS, and by treatment for the Initial and Maintenance Treatment Period (combined) for the AMS:

- Incidence of Serious TEAEs per 100 participant years by SOC, HLT, and PT
- Incidence of TEAEs Leading to Permanent Discontinuation of IMP per 100 participant years by SOC, HLT, and PT
- Incidence of TEAEs Leading to Study Discontinuation per 100 participant years by SOC, HLT, and PT
- Incidence of TEAEs Leading to Death by SOC, HLT, and PT
- Incidence of TEAEs by Maximum Relationship by SOC, HLT, and PT
- Incidence of Serious TEAEs by Relationship SOC, HLT, and PT – Note: For EudraCT reporting purposes
- Incidence of TEAEs Leading to Death by Relationship by SOC, HLT, and PT – Note: For EudraCT reporting purposes
- Incidence of TEAEs by Maximum Intensity, SOC, HLT, and PT
- Incidence of TEAEs by decreasing frequency of PT
- Incidence of TEAEs Above Reporting Threshold of 5% by SOC and PT
- Incidence of Non-Serious TEAEs by SOC, HLT, and PT

- Incidence of Non-Serious TEAEs by Maximum Relationship SOC, HLT, and PT
- Incidence of Non-Serious TEAEs Above Reporting Threshold of 5% by SOC and PT
- Incidence of Non-Serious TEAEs Above Reporting Threshold of 5% by Relationship SOC and PT
- Incidence of Related TEAEs by SOC, HLT, and PT
- Incidence of Related TEAEs Above Reporting Threshold of 5% by SOC and PT

The following summary will be provided by treatment for the ITP for the SS:

- Incidence of TEAEs Above Reporting Threshold of 5% with Risk Differences by SOC and PT
- Incidence of Serious TEAEs and Risk Differences by SOC and PT

The tables with risk differences will also be accompanied by figures (dot plots) which show the incidence of the AEs and corresponding 95% risk difference CIs. These will be ordered by descending order of risk difference (bimekizumab vs placebo).

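### The Wald risk-difference intervals in SAP 4.2.2 and 4.5.2.1 are too narrow when 0 of 30 placebo participants respond or have the event; the superiority tests are unaffected

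*SAP*

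**What the plan says.** **Efficacy.** SAP 4.2.2 gives the co-primary risk difference a large-sample interval: "Risk difference and associated 95% CI based on the Wald asymptotic between bimekizumab and placebo will be provided". If an arm has no or very few responders, the test changes and one interval is withdrawn: "Fisher's exact method will be applied instead, odds ratio and associated 95% CI will not be provided". Nothing in that rule alters the risk-difference interval. The Amendment 2 entry in the SAP version history confirms the intent: "the risk difference and its 95% will still be provided". For the key secondary endpoints SAP 4.3.1.2 says: "The primary analysis will be based on the CMH test as specified in Section 4.2.2".

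**Adverse events.** SAP 4.5.2.1 writes out the unpooled standard error and adds: "For the risk difference CIs calculated in this SAP, 1.96 will be used". That is also a Wald interval. It feeds three sets of outputs for the Initial Treatment Period:
- the table of TEAEs above a 5% reporting threshold, with its dot plot (SAP 4.5.2.2);
- "Incidence of Serious TEAEs and Risk Differences by SOC and PT", with its dot plot and no stated threshold (SAP 4.5.2.2);
- the safety-topics table and figure, also with no stated threshold (SAP 4.5.2.4).

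Planned arm sizes are 90 and 30 (SAP 1.2). The visible text names no score, exact or continuity-corrected interval for a risk difference.

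**The concern.** The Wald variance is the sum of p(1−p)/n over the two arms. When the observed placebo proportion is 0, its term vanishes, and the interval treats the placebo rate as known to be exactly zero. Thirty participants with no event do not show that.

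The SAP foresees this case for efficacy: it gives up the CMH test and the odds-ratio interval. It keeps the one interval that fails for the same reason, and that interval then stands alone beside the Fisher p-value.

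Two things are at stake. One is the stated precision, and mainly the lower limit, of the efficacy risk difference. The other is safety displays in which an interval clear of zero reads as a signal although the data are compatible with no difference.

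**Working it through.** **Inputs.** n = 90 and 30 (SAP 1.2). Multiplier 1.96 and unpooled SE (SAP 4.5.2.1). The documents give no placebo response rate, bimekizumab response rate or event rate that can be used here, so all true rates below are assumptions shown as ranges. The plan states no interval to reproduce.

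**1. How often placebo is 0/30.** (1−p)^30 = 74%, 55%, 40% and 21% for true rates of 1, 2, 3 and 5%.

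**2. Efficacy interval, 80/90 versus 0/30.** The risk difference is 88.9%.
- Wald: SE = √(0.8889 × 0.1111/90 + 0) = 0.0331; 88.9 ± 1.96 × 3.31 = 82.4 to 95.4%.
- Newcombe: the Wilson limits are 80.7 to 93.9% for 80/90 and 0 to 11.4% for 0/30 (upper limit 3.84/33.84). Lower limit = 88.9 − √(8.15² + 11.35²) = 74.9%. Upper limit = 93.9%.
- Miettinen-Nurminen: 76.9 to 93.9%.

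The Wald lower limit is 5.5 to 7.5 points higher than the score-type limits. At 90/90 versus 0/30 the Wald interval collapses to 100 to 100%.

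**3. Efficacy coverage**, by full enumeration of both binomials over true rates of 80, 85, 90 and 95% versus 1, 2, 3 and 5%. Wald covers 86 to 94%; it is 91 to 94% at bimekizumab rates of 80 to 85%, and lowest (86.2%) at 95% versus 3%. Newcombe covers 93 to 96%. The Wald error is one-sided: at 90% versus 2% the whole interval lies above the true difference 10.5% of the time, against a nominal 2.5%.

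**4. Adverse events with 0/30 on placebo.** The Wald lower limit exceeds zero when p/(1−p) > 3.84/90, that is p > 3.84/93.84 = 4.1%, or at least 4 of 90.

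| Events of 90 | Wald, % | Newcombe, % | Miettinen-Nurminen, % | Fisher p |
|---|---|---|---|---|
| 3 | −0.4 to 7.0 | −8.2 to 9.3 | −8.2 to 9.3 | 0.57 |
| 4 | 0.2 to 8.7 | −7.2 to 10.9 | −7.1 to 10.9 | 0.57 |
| 5 | 0.8 to 10.3 | −6.2 to 12.4 | −6.0 to 12.3 | 0.33 |
| 10 | 4.6 to 17.6 | −1.3 to 19.3 | −0.6 to 19.2 | 0.065 |
| 11 | 5.5 to 19.0 | −0.3 to 20.6 | 0.5 to 20.6 | 0.063 |
| 12 | 6.3 to 20.4 | 0.7 to 21.9 | 1.6 to 21.9 | 0.036 |

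The methods disagree for 4 to 11 events (4 to 10 by Miettinen-Nurminen). Since 4/90 = 4.4% and 5/90 = 5.6%, the 5%-threshold outputs are touched only from 5 events.

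**5. Chance that the Wald interval lies wholly above zero when both arms share the same true risk** (nominal 2.5%).

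| True risk | Any count | At least 5/90 |
|---|---|---|
| 1% | 1.0% | 0.2% |
| 2% | 5.8% | 1.9% |
| 3% | 11.4% | 5.4% |
| 5% | 14.3% | 10.2% |
| 10% | 7.0% | 6.9% |

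Newcombe stays below 1% in every row.

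**The case against.** The other side has several good points.

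- **No hypothesis decision moves.** A reader might infer that the co-primary or key secondary conclusions are at risk. They are not: superiority rests on the CMH or Fisher p-value, and in the 80/90 example all three lower limits are far from zero. This stands in full.
- **4/90 does not reach the general table.** A reader might infer that any preferred term at 4/90 versus 0/30 shows up as a signal. The 5% threshold keeps it out of the main TEAE table and plot. It can appear only as serious events of one term or in the safety-topics outputs.
- **Exclusion of zero is not always wrong.** From 12/90 all methods agree. A true excess may also exist: Protocol 2.3 lists oral candidiasis among the commonest events on bimekizumab. The error rates in step 5 are conditional on equal true risk, and 5% is the worst of the rates tabulated.
- **Zero on placebo is not certain.** The documents give no rate, and at 3 to 5% a zero count is less likely than not.
- **Scope.** A reader might extend the point to the P-SIM endpoints or to every risk difference in the trial. The visible text defines no P-SIM risk difference, and some sensitivity and secondary text is not shown.
- **The adverse-event formula was chosen deliberately**, to match the programme convention (SAP version history, version 1.3). The error mainly over-flags harm on bimekizumab, and no decision rule depends on it.

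These points narrow the concern. They do not make an interval labelled 95% perform at 95%.

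**Conclusion.** The concern holds for the risk-difference intervals in SAP 4.2.2, in 4.3.1.2 by reference, and in 4.5.2.1. With 0/30 on placebo the Wald interval ignores placebo uncertainty. For efficacy, this overstates the lower limit by 5.5 to 7.5 points in the 80/90 example, and overall coverage is about 86 to 94% at assumed true rates of 80 to 95% versus 1 to 5%. For safety, zero is excluded where score-type and exact methods do not exclude it: for about 5 to 11 of 90 in the 5%-threshold outputs, and from 4 of 90 in the serious-TEAE and safety-topics outputs.

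This is a defect in reported precision and in safety displays. It does not threaten the superiority tests or the control of Type I error for H1 to H4. The sizes rest on the planned 90 and 30 and on the assumed rates; the zero variance term follows from the SAP formula alone.

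**What to change.** Name one score-type interval, Miettinen-Nurminen or Newcombe, for the risk differences in SAP 4.2.2, 4.3.1.2 and 4.5.2.1. State that it also applies when an arm has no responders or no events, and that the dot plots use it. Replace the standard-error and interval formulas in 4.5.2.1 to match.

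The change needs SAP wording and a different interval calculation. No test, alpha allocation or data collection changes. The costs are wider intervals and adverse-event intervals that no longer match the programme convention. If comparison with earlier studies matters, keep the Wald interval as a labelled supplementary column.
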